### **7.3 Effectiveness Endpoint**

The primary endpoint is achievement of distance corrected near visual acuity (DCNVA) of Snellen equivalent 20/40 or better (at 40 cm) and at least 10 letters (ETDRS) improvement in DCNVA in the primary eye.

This endpoint will be evaluated against two objectives, a) 75% or more of primary eyes achieve the effectiveness endpoint at 12 months postoperative and, b) the percentage of primary eyes achieving the effectiveness endpoint at 6 months postoperative (6-month responder rate) is higher than the percentage in the randomized control group.

## **7.4 Analysis of Safety Data**

Safety data analyses will be performed and separate summaries will be provided for primary and all eyes. Descriptive statistics on the following attributes will be provided:

- BCDVA
- IOP
- Slit Lamp findings
- Fundus exam findings
- Rate of adverse events

## **7.5 Study Population**

A total of 360 subjects who meet the following criteria will be enrolled and determined eligible in this study:

### **7.5.1 Inclusion Criteria**

1. Subjects must be between ages of 45 to 60 at the time of enrollment.
2. Subjects must have best corrected distance visual acuity (BCDVA) of 20/20 in each eye.
3. Subjects must have distance corrected near visual acuity (DCNVA) @ 40 cm of 20/50, 20/63 or 20/80 in each eye.
4. Subjects must have uncorrected near visual acuity (UCNVA) @ 40 cm of 20/50, 20/63 or 20/80 in each eye.
5. Subjects must have preoperative manifest refraction spherical equivalent (MRSE) in each eye of -0.75 to +0.50 diopters with no more than 1.00 diopter of astigmatism. The difference between the MRSE and cycloplegic refraction spherical equivalent (CRSE) should be  $\leq 0.50$  diopter.
6. Subjects must require a minimum add of +1.25 or greater to read 20/20 at near (40 cm).
7. Subjects must be phakic in each eye.
8. Subjects must be alert, mentally competent, and able to understand and comply with the requirements of the clinical study, and be personally motivated to abide by the requirements and restrictions of the clinical study. Patients must be available for the follow-up period.
9. Subjects must be able to provide written informed consent.

### **7.5.2 Exclusion Criteria**

1. Subjects where either pupil has a baseline percent change from scotopic to photopic of less than 30% or an absolute difference of less than 1.00 mm between scotopic and photopic pupil size as measured by the NeuroOptics Pupillometer.

2. Subjects with ocular inflammation, chronic uveitis, or other recurrent anterior or posterior segment inflammatory conditions in either eye; subjects with any ocular or systemic disease(s) posing a significant risk for ocular inflammation, including but not limited to autoimmune disorders (e.g., rheumatoid arthritis, ankylosing spondylitis, Reiter's syndrome, ulcerative colitis, Crohn's disease, psoriasis, sarcoidosis, Behcet's disease), infections (toxoplasmosis, cat-scratch fever, West Nile virus, syphilis, tuberculosis, herpes zoster, herpes simplex, adenovirus), ocular trauma, or gout.
3. Subjects with scleral thickness of less than 530 microns as measured 3.5 to 4.0 mm posterior to the superior temporal quadrant limbus in either eye.
4. Subjects with a history of any prior intraocular procedure (e.g., corneal transplant, filtering procedures for glaucoma, vitrectomy, retinal detachment repair, cataract surgery) or any prior refractive procedure (e.g. LASIK, surface excimer, or incisional surgery) in either eye.
5. Subjects with any history of prior extraocular muscle surgery or orbital surgery.
6. Subjects with chronic ocular disease, including but not limited to corneal pathology, primary or secondary glaucoma, iritis, herpes simplex, uveitis, trachoma, ocular pemphigoid, Sjogren's disease, uveal melanoma, Thyroid Related Immune Orbitopathy or clinically significant retinal pathology in either eye.
7. Subjects with any acute ocular disease that has not been completely treated and resolved for at least three months such as conjunctivitis, blepharitis, chalazion, corneal abrasion or keratitis in either eye.
8. Subjects with chronic systemic diseases which may affect the eye, including but not limited to diabetes, ulcerative colitis, systemic lupus erythematosus, Crohn's disease, collagen vascular disease, rheumatoid arthritis, any bleeding diathesis, or systemic manifestations of HIV/AIDS. Any other uncontrolled systemic disease (e.g., hypertension, cancer, etc.) that could compromise the patient's participation.
9. Use of any medication, such as coumadin, that could make the surgical procedure more difficult. Subjects using Coumadin, aspirin or NSAID medication under orders from a doctor must be able to provide written approval from the treating doctor for discontinuing this medication at least ten (10) days prior to surgery.
10. Subjects with chronic ocular surface disease, including but not limited to subjects with a prior diagnosis of chronic dry eye syndrome based on tests such as but not limited to, corneal or conjunctival staining, Ocular Surface Disease Index symptom score or Schirmer tear testing.
11. Subjects who are allergic to any medications used in the protocol.
12. Subjects who are pregnant, lactating, or of child-bearing age and not practicing a medically approved method of birth control

## **8.0 STUDY METHODS**

### **8.1 Patient Screening and Enrollment**

Prior to enrollment in the study, interested subjects will be screened to determine initial eligibility. The investigator or a designee will explain the study purpose and summary procedures and subject responsibilities to the potential subject. If it appears that the subject is interested and may be a candidate for the study, the subject will be asked to review and sign a Screening Informed Consent. The Screening Informed Consent provides a summary of the preliminary screening testing which will include standard of care testing including a medical history, vision testing and an examination of ocular health.

If preliminary eligibility is met, the subject will be asked to sign a Study Informed Consent Form which describes the surgical procedure; the potential benefits and risks, study examinations to be conducted, the frequency of follow-up visits, the expense reimbursement to be provided to the subject as well as other topics. When the Study Informed Consent is signed by the subject and by the Investigator or designee, the Subject is considered to be enrolled. Additional study specific testing of the subject's ocular and medical condition as specified in the baseline examination will be performed to determine eligibility. If during this testing, the Investigator or Sub-Investigator determines that the subject will not meet the protocol inclusion or exclusion criteria the examination may be terminated.

If the subject satisfies all inclusion and exclusion criteria, the full baseline examination data will be provided to the Sponsor for verification that all data have been obtained and meets eligibility criteria. Upon approval by the Sponsor, the subject will be scheduled for surgery if the subject has been enrolled and determined to be eligible at an Investigational site that is participating in the non-randomized cohort.

If the subject has been enrolled and determined to be eligible at an Investigational site that is participating in the randomized controlled sub-study, the subject will be randomized (1:1 ratio) to either the surgery group or the control group. Subjects randomized to the control group will be followed for 6 months, and will be eligible to undergo VisAbility Implant surgery after completion of the six month observation period.

### **8.2 Clinical Parameters and Examination Schedule**

The clinical parameters to be recorded at baseline and post-operative examinations are shown in Table 1: Schedule of Visits and Measurements on the following page.

**TABLE 1: SCHEDULE OF VISITS AND MEASUREMENTS**

	Initial										Follow-up	
	Pre-Op	0 Day	1 Day	1 Week	1 Month	2 Months	3 Months	6 Months	12 Months	18 Months	24 Months	
Slit Lamp Biomicroscopy OD, OS	✓ 		✓	✓	✓	✓	✓	✓	✓	✓	✓	✓
Applanation Tonometry OD, OS	✓ 		✓	✓	✓	✓	✓	✓	✓	✓	✓	✓
Gonioscopy OD, OS	✓								✓			
Scleral Thickness Measurement OD, OS	✓											
Implant Assessment OD, OS			✓	✓	✓	✓	✓	✓	✓	✓	✓	✓
Axial Length / ACD OD, OS	✓								✓			✓
Corneal Topography / Keratometry OD, OS	✓											
Pupillometry OD, OS	✓ 	✓	✓	✓	✓	✓	✓	✓	✓	✓	✓	✓
Posterior Pole exam with 78 /90D lens OD, OS	✓ 		✓		✓	✓	✓	✓		✓		
Dilated Indirect Ophthalmoscopy 20/30D lens OD, OS	✓			✓					✓			✓
Visual Fields OD, OS	✓											
Cup/Disk Ratio OD, OS	✓								✓			✓
Cycloplegic Refraction w/ VA OD, OS	✓								✓			✓
Manifest Refraction OD, OS	✓			✓ 	✓	✓	✓	✓	✓	✓	✓	✓
BCDVA OD, OS	✓ 			✓	✓	✓	✓	✓	✓	✓	✓	✓
UCDVA OD, OS	✓		✓ 	✓	✓	✓	✓	✓	✓	✓	✓	✓
UCNVA @ 40 cm OD, OS, OU	✓						✓	✓	✓	✓	✓	✓
UCIVA @ 66 cm OU	✓						✓	✓	✓	✓	✓	✓
DCNVA @ 40 cm OD, OS, OU	✓				✓	✓	✓	✓	✓	✓	✓	✓
Patient Preferred Distance DCN - OD, OS, OU UCN - OU	✓						✓	✓	✓	✓	✓	✓
Minimum add to achieve 20/20	✓						✓ 					
NAVQ (Validated PRO) & Patient Questionnaire	✓							✓	✓	✓	✓	✓
Sub-Study Only Wavefront measurements 	✓						✓	✓	✓	✓	✓	✓
Sub-Study Only Defocus Curve 	✓						✓	✓	✓	✓	✓	✓

Visual acuity will be measured using pinhole on day 1

Fellow Eye Safety Exam (when fellow eye surgery is 61-180 days after primary eye surgery)

Randomized Sub-study subjects only – control group subjects are examined through 6 months and the surgery group through 24 months.

Measure BCDVA using baseline refraction

Examination methods are provided in Appendix 1: Examination Methods.

[REDACTED]

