### **7.2 Study Design**

This is a prospective multicenter clinical study that will enroll and determine eligible 360 subjects ranging in age between 45 and 60 years of age with distance corrected near visual acuity (DCNVA) and uncorrected near visual acuity (UCNVA) of 20/50 to 20/80 (inclusive). Subjects will be enrolled at up to 14 clinical sites with no site enrolling and determining eligible more than 20% of the 360 eligible subject cohort. A PMA application will be submitted when all study subjects have completed 12 months of follow-up.

Subjects will be consented and screened based on medical history, ocular history and visual acuity criteria. Subjects will be required to satisfy specific inclusion and exclusion criteria during a baseline examination to be eligible for surgery. Subjects will be implanted with the VisAbility Implant [REDACTED] in the dominant eye, which will be designated as the primary eye. The fellow eye will be implanted no sooner than 14 days after the primary eye and only in the absence of unresolved adverse events in the primary eye. Subjects primary eye will be examined at one day, one week and at 1, 2, 3, 6, 12, 18 and 24 months post-operatively. The fellow eye will be examined at one day, one week and one month postoperatively. The one week and one month examinations of the fellow eye may be combined with visits for the primary eye if the visit windows permit. After the fellow eye one month visit, the fellow eye will be examined in accordance with the subsequent primary eye examination visits. A validated Patient Reported Outcome Measurement instrument [REDACTED] will be given to all enrolled and eligible subjects pre-operatively and at 6, 12, 18 and 24 months.

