## 8.5 Scheduled Post-Operative Visit Schedule

### 8.5.1 Primary Eye Visit Schedule

Subjects enrolled and eligible in the non-randomized cohort of the study and subjects enrolled, eligible and assigned to the randomized surgery group will be examined according to the following schedule based on the date of primary eye surgery. Surgery on the primary eye may not occur more than 60 days after a baseline examination establishing eligibility. Visit windows are calculated on a 30 day month.

Pre-operative Baseline Evaluation	(Day -60 to Day -1)
Surgery	(Day 0)
One Day Exam	(18 to 36 hours)
One Week Exam	(7 days +/- 2 days)
One Month Exam	(1 month +/- 7 days)
Two Month Exam	(2 months +/- 14 days)
Three Month Exam	(3 months +/- 14 days)
Six Month Exam	(6 months +/- 21 days)
Twelve Month Exam	(12 months +/- 45 days)
Eighteen Month Exam	(18 months +/- 45 days)
Twenty-four Month Exam	(24 months +/- 60 days)

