### **8.5.3 Fellow Eye Visit Schedule**

Subjects undergoing surgery in the fellow eye will be examined according to the following visit schedule. The one week and one month examinations may be combined with visits for the primary eye if the visit windows permit. After the one month visit, the fellow eye will be examined at the same time as scheduled follow-up visits for the primary eye.

Surgery	(Day 0)
One Day Exam	(18 to 36 hours)
One Week Exam	(7 days +/- 2 days)
One Month Exam	(1 month +/- 14 days)

If the fellow eye surgery is 61 to 180 days after the primary eye surgery, the fellow eye will be examined postoperatively after the one month visit, on a separate visit schedule for the 3 and 6 month visits only, established based on the same intervals and visit windows as shown above for the primary eye. Subsequent to the 6 month visit, the fellow eye will be examined at the same visit as the primary eye. Fellow eye and OU data will be recorded as attributable to the fellow eye visit timing through the fellow eye 6 month postoperative visit.

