### **8.5.4 Fellow Eye Supplemental Baseline Examination**

Fellow eye surgery may be performed 61 to 180 days after the baseline examination that has determined eligibility if a safety exam is performed and the findings do not alter the subject's continued eligibility. The following clinical parameters will be evaluated in the safety exam:

1. Medical history

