2. BCDVA
2. Slit lamp biomicroscopy
3. Goldmann tonometry
4. Pupillometry
5. Posterior pole examination.

If fellow eye surgery is to be performed 181 days or more after a baseline exam determining eligibility, a complete baseline examination must be repeated. Baseline efficacy data for the fellow eye and for OU will always be from the baseline examination established prior to the primary eye surgical intervention.

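### Table 1 footnote 2 counts the 61-180 day window for the fellow-eye safety exam from primary eye surgery, while Section 8.5.4 counts it from the eligibility baseline

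*Combined protocol and SAP*

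**What the plan says.** Table 1 (Schedule of Visits and Measurements) attaches footnote 2 to the Pre-Op tick of five rows: slit lamp, tonometry, pupillometry, posterior pole and BCDVA. The footnote reads "Fellow Eye Safety Exam (when fellow eye surgery is 61-180 days after primary eye surgery".

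Section 8.5.4 sets the condition for operating on the second eye: "Fellow eye surgery may be performed 61 to 180 days after the baseline examination that has determined eligibility if a safety exam is performed". A further condition on that exam is that "the findings do not alter the subject's continued eligibility". The section lists medical history plus the same five ocular items. For later surgery, "181 days or more after a baseline exam determining eligibility, a complete baseline examination must be repeated".

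Three other provisions fix the possible dates:

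- Section 8.5.1: "Surgery on the primary eye may not occur more than 60 days after a baseline examination establishing eligibility". Its schedule places the baseline at Day -60 to Day -1.
- Section 7.2: "The fellow eye will be implanted no sooner than 14 days after the primary eye". The same section permits second-eye surgery "only in the absence of unresolved adverse events in the primary eye".
- Section 8.5.3: "If the fellow eye surgery is 61 to 180 days after the primary eye surgery, the fellow eye will be examined postoperatively" on its own schedule for the 3 and 6 month visits. This uses the primary-surgery clock, but for visits after fellow-eye surgery.

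**The concern.** One exam has two start dates. The day range and the ocular items match, so the footnote and Section 8.5.4 are evidently describing the same requirement, yet they trigger it at different times. Section 8.2 sends sites to Table 1 for the parameters to record, and the footnote does not point to Section 8.5.4.

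Under Section 8.5.4 the safety exam, or from day 181 the full repeat baseline, is a precondition of elective surgery on a second eye. A site working from the table could miss either one without realising that it had deviated. Two things are at stake:

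- **Early second surgeries:** the medical-history update and the documented decision that the subject remains eligible.
- **Late second surgeries:** the full repeat baseline. Table 1 marks scleral thickness, corneal topography/keratometry and visual fields at Pre-Op only, so no routine visit repeats them.

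Fellow eyes belong to the Safety Cohort (Section 11.4).

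**Working it through.** **Inputs**

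- b = days from baseline to primary surgery, 1 to 60 (Section 8.5.1).
- d = days from primary to fellow surgery, at least 14 (Section 7.2).
- Section 8.5.4 counts b + d: up to 60, no extra exam (by implication); 61 to 180, safety exam; 181 or more, complete baseline.
- Footnote 2 counts d alone: safety exam if d is 61 to 180.

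**Early conflict** (Section 8.5.4 requires the safety exam, the footnote does not): d ≤ 60 and b + d ≥ 61, so b ≥ 61 − d.

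**Late conflict** (Section 8.5.4 requires a complete baseline, the footnote shows only the short exam): 61 ≤ d ≤ 180 and b + d ≥ 181, so b ≥ 181 − d.

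| d | Footnote 2 | b in conflict | Baseline dates in conflict (of 60) | b + d in those cases |
|---|---|---|---|---|
| 14 | none | 47-60 | 14 | 61-74 |
| 30 | none | 31-60 | 30 | 61-90 |
| 60 | none | 1-60 | 60 | 61-120 |
| 61 to 120 | short exam | no permitted b | 0 | – |
| 121 | short exam | 60 | 1 | 181 |
| 150 | short exam | 31-60 | 30 | 181-210 |
| 180 | short exam | 1-60 | 60 | 181-240 |

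**Longest interval from baseline to fellow surgery**

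- No safety exam: 60 days under Section 8.5.4; 60 + 60 = 120 days if scheduled from the footnote.
- Short exam only: 180 days under Section 8.5.4; 60 + 180 = 240 days if scheduled from the footnote.

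**Reverse direction.** For d of 61 to 180, b + d is at least 1 + 61 = 62, so Section 8.5.4 always requires the safety exam or more. The footnote never asks for more than Section 8.5.4. A site that follows Section 8.5.4 therefore satisfies both; a site that follows the footnote may not.

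**Whole grid.** For d from 14 to 180 and b from 1 to 60 there are 167 × 60 = 10,020 date pairs. Early conflicts: 14 + 15 + … + 60 = 1,739. Late conflicts: 1 + 2 + … + 60 = 1,830. Together 3,569. These counts weight every pair equally and do not forecast how many subjects are affected.

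**The case against.** The strongest reply is that this is a loosely worded footnote and not a second rule. It labels ticks in a table. It does not authorise surgery, does not say that the exam is unnecessary at day 60 or before, and does not say that a short exam suffices from day 181. Only Section 8.5.4 sets conditions, and following it breaks nothing. The 120 and 240 day figures arise only for a site that ignores that section. This stands as a limit on the weight of the point. It does not remove the conflict, because no visible text ranks the section above the table.

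At the late end, Table 1 as shown has no medical-history row, so a site triggered by the footnote should open Section 8.5.4 and find the 181-day rule there. That lowers the late risk. But the footnote carries no cross-reference, and a site could complete the five ticked items and think itself finished. At the early end the footnote triggers nothing, so the argument gives no help.

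Routine visits largely cover the short exam, and this stands. In rows labelled for both eyes, Table 1 shows four of the five ocular items at 1 Day and BCDVA at 1 Week (day 5 to 9), all before the earliest fellow surgery at day 14. All five recur at 1 Month and at 2 Months (60 ± 14, day 46 to 74). Section 8.5.4 sets no limit on how recent the exam must be. What remains uncovered early is the history update and the eligibility decision.

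Section 8.5.3 does use the primary-surgery clock, but only for post-operative visits. It may explain where the footnote's wording came from; it does not support it.

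Finally, text is redacted directly after Table 1 and in Section 9.0, so scheduling instructions may exist that cannot be seen. That is a fair caution.

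**Conclusion.** The inconsistency holds and is minor. At d = 60 the two rules disagree for every permitted baseline date on whether a safety exam is needed. At d = 180 they disagree for every permitted baseline date on whether the short exam is enough. In between, the conflict depends on the age of the baseline, and for d of 61 to 120 there is none.

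The conclusion assumes the Day -60 to Day -1 baseline window, the 14-day minimum between surgeries, and that nothing in the redacted text reconciles the clocks. The documents give no expected intervals between baseline, first and second surgery, so the number of subjects affected cannot be estimated.

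The consequence is confined to pre-operative checks on the second eye, and Section 7.2 separately bars that surgery while primary-eye adverse events are unresolved. The primary-eye endpoints, sample size and significance level are unaffected. Fellow-eye and binocular efficacy baselines are also unaffected, since Section 8.5.4 fixes them at the examination before primary surgery whichever clock applies.

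**What to change.** Reword footnote 2 along these lines: *Fellow-eye safety exam: required if the fellow eye is operated on 61-180 days from the eligibility baseline; from day 181, repeat the complete baseline (see 8.5.4).* Leave Section 8.5.3 as it is, because its primary-surgery clock is right for post-operative visits. The new wording also fits control subjects who cross over to surgery, whose baseline is the 6 month visit (Section 8.5.2).

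The cost is one footnote. Some second-eye surgeries that a site would have scheduled from the table will now visibly need a safety exam, or a repeat baseline if late, but Section 8.5.4 already requires both. The safety exam can be done at a scheduled visit.

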#### **8.4 Post-Operative Care**

Following surgery, physicians should adhere to the following guidelines of topical ophthalmic medications and care:

- To help control pain postoperatively, an icepack should be applied to the eye at intervals for approximately 30 minutes or longer as needed. A topical non-steroidal anti-inflammatory drug (NSAID) such as nepafenac ophthalmic suspension or equivalent may also be instilled immediately postoperatively. Chilled BSS may be instilled every 15 minutes and topical steroid drops such as prednisolone acetate 1% ophthalmic suspension or equivalent may be used every 15 to 30 minutes until the pupil reaction is greater than 25% as described in the next step. Prior to discharge the patient should be given Diamox 500mg Sequel PO or equivalent.

- Pupil functionality will be evaluated postoperatively using a NeurOptics Pupillometer every 15 to 30 minutes until the percent pupil constriction reading is at least 25%. A second, confirmatory reading may be taken as soon as 5 minutes after the first. If two pupil constriction readings of at 25% or greater are not achieved within the first 4 hours after surgery, preparation for removal of the implant segments will commence. The Investigator must remove all four implant segments no later than 6 hours after the surgery if two pupil constriction readings of 25% or greater are not achieved within 6 hours postoperatively.
- During the first week after the surgery, antibiotic drops such as moxifloxacin ophthalmic solution or equivalent and a topical steroid such as Lotemax gel or equivalent should be instilled in the eye. Additionally, NSAIDs such as topical nepafenac ophthalmic suspension or equivalent and / or oral medications such as naproxen or equivalent or acetaminophen with codeine or equivalent may be given as needed for pain during this time.
- Absorbable and / or non-absorbable conjunctival sutures may be removed at one week post-operatively or later as needed.

